- 3. Outpatients will be referred from other healthcare facilities, the community, or the treating physician.

Once referred, study staff will approach subjects who retain decision-making capacity, or the authorized representative of a patient who lacks decision-making capacity, for permission to complete a screening for possible enrollment. Please note that clearance for consent will follow standard clinical procedures. A co-investigator/coordinator will review with the potential subject/authorized representative the informed consent form, and clearly explain all the procedures and risks of the testing. The subject/authorized representative will be encouraged to ask questions, both during the initial interview and throughout the study. The PI or a co-investigator/coordinator will answer any questions regarding the study during the consent process. During the enrollment interview, the subject/authorized representative will be instructed not to take any prescribed or over-the-counter herbal supplements or nutraceuticals during participation in this study to avoid potentially confounding study results. Once enrolled, the subject may terminate his/her participation at any time during the study.

VIII. STUDY PROCEDURES

Study Design:

This is a randomized, double-blind, placebo-controlled phase II study. We plan to enroll 30 subjects with moderate to severe TBI (Huperzine = 15, Placebo = 15). Subjects may be inpatients or outpatients. Subjects will receive study drug or placebo for 12 weeks, and follow-up will continue through Week 52. Subjects enrolled in this study will receive standard acute and rehabilitative care. All subjects will be enrolled at Spaulding. Spaulding inpatient subjects who are discharged from Spaulding prior to closure of the active treatment window (at week 12) will continue to be followed either by telephone or in-person. Weekly phone calls between the study coordinators and subjects (or their authorized representative) will ensure that, for each subject actively enrolled, the dosage of study medication is correct, any new adverse events (including seizure) have been captured and any concerns raised by the subject or study staff have been addressed.

Recruitment and Consent

SRH Inpatients

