On a weekly basis during the 12-week active treatment period, study staff will record medication changes that have occurred since the previous week. For inpatient subjects, study staff will conduct a structured chart review and speak with the treating physician/nursing staff to identify any medication changes. For outpatient subjects, medication monitoring will be conducted through weekly phone calls. In addition to recording medication changes that have occurred over the last week, changes in baseline symptoms, side effects from Huperzine-A, adverse events and episodes of seizure activity that may have occurred in the intervening week will also be recorded. Approximately every three months after the 12-week active treatment phase (i.e., week 24, week 36, week 52), subjects will be monitored for the occurrence of any new *serious* adverse events as well as any unresolved/unstable AEs that may have occurred during the 12-week treatment period. Subjects will be instructed to call the Study Coordinator if a serious adverse event occurs between scheduled follow-ups. Serious adverse events will be reported immediately, in accordance with DSMB and IRB policies.

Drug Administration and Dosing:

Within 7 days of completion of the baseline assessment, subjects will receive the initial dose of the study drug (Huperzine A or placebo). The study drug will be prepared and stored by a third-party vendor and will be shipped to the Spaulding pharmacy. Due to changes in Massachusetts State Laws compounding pharmacies are now required to prepare and label the study drug for each individual subject. The shelf life of the study drug has been reduced from one year to six months. The study drug will be couriered to SRH hopefully, within 24 hours of receiving the prescription. Thus, the window between randomization and first dose of study drug has been increased to seven days. The randomization list will be maintained by a Spaulding pharmacist with no access to subjects or study data. Please see Appendix I for more detailed drug administration guidelines. For inpatient subjects, the study drug will be administered by nursing staff. For outpatients, instructions will be given to the subject and/or caretaker on how to continue the dosage schedule. Weekly phone calls will be made to ensure compliance.

Dose Titration:

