Potential side effects of Huperzine A include: nausea, vomiting, diarrhea, sweating, blurred vision, slurred speech, loss of appetite, contraction and twitching of muscle fibers, cramping, increased saliva and urine, inability to control urination (incontinence), hypertension, and slowed heart rate (bradycardia) [36]. As with any investigational agent, there may be side effects that are unknown that may occur.

Neuropsychological assessments/questionnaires:

There are no risks involved with the neuropsychological testing batteries used in this study. If the subject feels uncomfortable answering any of the questions or performing any of the neuropsychological assessments, he/she may stop at any time. If the subject becomes bored or fatigued while completing the battery, he/she may be able to take a break and rest before completion.

Expected symptoms of Traumatic Brain Injury:

Based on the severity of the subject's TBI, there are many different symptoms expected that are related to the injury. Thus, these symptoms can change as the patient's injury status progresses from the acute to chronic phase. These expected symptoms may include medical (e.g., hemodynamic changes, fever, dysautonomia), cognitive (e.g., confusion, distractibility, memory impairment) and behavioral (e.g., agitation) problems. Please see Appendix A for the list of adverse events frequently seen in the TBI population.

In order to determine whether side effects seen during the study are related to TBI or Huperzine A, we will review baseline symptoms of TBI for the patient prior to starting Huperzine A, monitor for exacerbation of existing symptoms and assess for the onset of new symptoms through systematic medical record review, medication/seizure/side effects checklists and also through contact with the subject and treating physician/nursing team.

Data Safety Monitoring Board and stopping rules:

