- Medication Log: Prior to randomization, study staff will review the results of screening tests to identify potential drop-outs; subjects identified as being at high risk for noncompliance with study drug will not be randomized. For Spaulding inpatients, nursing staff will maintain a treatment record which will be checked weekly by study staff, and transcribed onto a medication log which will include the time, date, and each dosage of Huperzine A taken. Finally, any deviation from adherence to the medicine regime will be documented. Study data will be monitored for irregularities. Any irregularities in the data will be investigated for possible deviations in adherence. We will also track the patient's other medications (not involving Huperzine) on this Log including dosing amounts and times. For community-dwelling outpatients, subjects and/or caretakers will be given a medication diary to fill out daily.
- Laboratory Data: Serum measures of renal and liver function will be obtained at baseline, 6 weeks, 12 and 13 weeks to evaluate for eligibility to participate in the study as well as any potential unexpected side effects. Hematologic data will also be obtained at baseline, 6 weeks, 12 and 13 weeks to observe for any side effects. A general chemistry panel will be completed at baseline. Clinical blood results obtained within 48 hours of the study time

points will be able to be used for evaluation thereby, reducing the number of venipunctures for the subject.

- Biomarkers: Blood samples for UCH-L1, GFAP, NF-l and Tau will be obtained at the time of enrollment, at 24 hours, 23 days, 30 days post injury and 90 days post injury. Deidentified samples will be shipped to Quanterix Corporation for analysis after processing by the SRH clinical lab. After analysis Quanterix Corporation will return the samples to the Spaulding Rehabilitation Network Research Institute.

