- Study Drug Blood Levels: Blood samples will be drawn from 10% of subjects to assess efficacy vs. steady- state HupA concentrations and tolerability during the maintenance phase. Samples will be drawn pre-dose and 1 hour post dose on Day 21 or Day <21 (at the end of dose escalation for each patient in the 10%, whatever dose they escalate to). During the maintenance phase a weekly pre-dose sample will be drawn. Week 12, on the last day of dosing, a pre-dose and 1 hour post-dose sample will be drawn. These samples will be processed in the SRH clinical labs, stored at -80, and then forwarded to the Illinois Institute of Technology Research Institute (IITRI) in Chicago. De-identified samples will be shipped to IITRI and the link to the code will remain at SRH and not be provided to IITRI.
- Baseline Symptom Checklist: This will be completed before study drug is started. After treatment is initiated, the study staff should use the baseline symptom checklist list as a reference to identify and code new symptoms that arise after treatment is initiated, or to detect an exacerbation of a previously-noted symptom. For Spaulding inpatients, these data will be collected from systematic medical record review and also from speaking with the treating medical/nursing staff on a weekly basis. For outpatient, changes in baseline symptoms will be monitored through weekly phone calls.
- Drug Side Effects Checklist: For Spaulding inpatients, the study staff will evaluate potential side effects of Huperzine A using the drug side effect checklist during weekly systematic review of the medical record. This scale covers all known possible side effects of Huperzine A. In addition to speaking with medical/nursing staff, the subjects/caregivers may be asked to report whether they have experienced any side effects in an open-ended manner, and any side effects experienced by patients will be marked on a scale of 1 through 3 to measure severity (1- Mild, 2- Moderate, 3- Severe). If any side effects are reported, the degree of relatedness to the Huperzine A intervention will be assessed. For outpatient, side effects from Huperzine-A will be monitored through weekly phone calls.

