- Seizure Log: Although it is not possible within the scope of this study to obtain definitive information regarding Huperzine A's anticonvulsant properties, a detailed seizure log will be utilized to evaluate for seizure events or signs associated with seizures in Spaulding inpatients. This log will be maintained weekly by the study staff collecting data through the systematic review of the medical record and speaking to the treating medical/nursing staff. Study staff will review documented chart evidence of seizure including any EEG that is performed as part of the routine medical care. For outpatient subjects, episodes of seizure activity will be monitored through weekly phone calls.

- Suicidality Scale We will monitor for suicidality using the Columbia-Suicide Severity Rating Scale (C-SSRS) at baseline, 6 weeks and 13 weeks as requested by the FDA Division of Neurology Products per our IND.
- Adverse event monitoring: In addition to the above, we will continually monitor for changes in patient health status. The baseline symptom checklist, side effect checklist and seizure log will be used to help monitor for changes in symptoms or side effects in Spaulding inpatients, and community-dwelling outpatients. For Spaulding inpatients, we will also monitor the patient's chemistry by the scheduled laboratory exams, and monitor compliance through the medication log. By using this multimodal approach, we will be able to appropriately rate events as they occur, and to accurately associate such events to the appropriate changes in subject status (ex. whether from TBI or Huperzine, expected or unexpected, etc). In addition, approximately every three months after the 12-week active treatment phase (i.e., week 24, week 36, week 52), subjects will be monitored for the occurrence of any new *serious* adverse events as well as any unresolved/unstable AEs that may have occurred during the 12-week treatment period. Subjects will be instructed to call the Study Coordinator if a serious adverse event occurs between scheduled follow-ups. Serious adverse events will be reported immediately, in accordance with DSMB and IRB policies.

Treatment Compliance:

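### Outpatient adverse events and seizures are collected mainly by a weekly call to the subject or, as an alternative, a representative; no informant is routinely asked as well, so events may be missed in a cognitively impaired population.

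*Combined protocol and SAP*

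**What the plan says.** Section VIII (Study Design) provides for "Weekly phone calls between the study coordinators and subjects (or their authorized representative"), covering dosage, new adverse events including seizure, and any concerns. The transition procedures in the same section move discharged inpatients to weekly calls too.

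Section XII sets the sources by care setting.

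- **Seizures.** For inpatients the log is kept by "collecting data through the systematic review of the medical record and speaking to the treating medical/nursing staff", with any routine EEG reviewed. Then: "For outpatient subjects, episodes of seizure activity will be monitored through weekly phone calls".
- **Side effects.** Inpatients have weekly record review and contact with staff, and "the subjects/caregivers may be asked to report whether they have experienced any side effects in an open-ended manner". The item then closes: "For outpatient, side effects from Huperzine-A will be monitored through weekly phone calls".
- **Caretaker records.** "For community-dwelling outpatients, subjects and/or caretakers will be given a medication diary to fill out daily". This diary records medication, not events.

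Section XI, on expected symptoms of TBI, states more generally that attribution of side effects will draw on baseline symptoms and on monitoring "through systematic medical record review, medication/seizure/side effects checklists and also through contact with the subject and treating physician/nursing team".

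After Week 12, sections VIII and XII provide for monitoring of serious and unresolved events at about Weeks 24, 36 and 52. Between these, "Subjects will be instructed to call the Study Coordinator if a serious adverse event occurs between scheduled follow-ups".

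**The concern.** Every subject enters with ongoing post-traumatic amnesia, a slow Trails B, or a poor self-reported memory or cognition score (section VI). For an outpatient who has decision-making capacity, the subject is the only respondent that the text names for the weekly call, because section VIII provides representatives for patients who lack capacity. An inpatient's events have a second, independent source in the chart and the nursing staff. An outpatient's events have no equivalent that the outpatient items require.

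Three uses of the data depend on complete counts. Secondary aim 2 compares the proportion with seizures by Fisher's exact test. Secondary aim 3 compares the frequency of adverse effects. The stopping rule in section XI acts on a disproportionate incidence of serious adverse events on active treatment, and that section gives a seizure without hospitalization as an example of an event usually considered serious. A missed seizure therefore affects safety oversight as well as an exploratory comparison.

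**Working it through.** The plan states no figure for reporting completeness, so there is none to reproduce. The check compares the sources, works out the contact intervals, and then shows what assumed completeness would do.

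**1. Sources set side by side**

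| Item | Inpatient | Outpatient or discharged |
|---|---|---|
| Seizures | Chart, staff, routine EEG | Weekly call |
| Side effects | Chart, staff; caregiver optional | Weekly call |
| Who is on the call | – | Subject, or a representative instead |
| Serious events between later contacts | Subject told to call | Subject told to call |

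The optional caregiver question stands in the inpatient part of its item, and the outpatient sentence does not repeat it. No item requires an informant in addition to the subject.

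**2. Contact intervals after dosing**

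Safety contacts fall at Weeks 13, 24, 36 and 52 (section VIII). The nominal gaps are 24 − 13 = 11, 36 − 24 = 12 and 52 − 36 = 16 weeks.

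**3. Equal under-reporting (completeness assumed)**

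Take 15 subjects per arm (section VI), true proportion p, completeness s in both arms, and one event per affected subject. Expected reported subjects = 15 × p × s.

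- p = 20%, s = 1: 15 × 0.20 = 3.0
- p = 20%, s = 0.90: 2.7
- p = 20%, s = 0.60: 1.8

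The ratio between arms does not change; the cost is lost events.

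**4. Unequal under-reporting, only if the drug alters recall**

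Apparent ratio = true ratio × (s active ÷ s placebo). All values of s are assumed.

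- True ratio 1.0: 0.90/0.80 = 1.125; 0.75/0.60 = 1.25; 0.70/0.50 = 1.40; 0.90/0.60 = 1.50.
- True seizure proportions 10% active and 20% placebo (ratio 0.50), at 0.90 and 0.60: 9% and 12%, ratio 0.75.

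Exact two-sided Fisher rejection at 15 per arm with no true difference:

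| True proportion | Complete reporting | 0.90 vs 0.60 | Extra reported subjects, active arm, 15 × p × 0.30 |
|---|---|---|---|
| 20% | 1.7% | 2.2% | 0.9 |
| 40% | 1.6% | 4.6% | 1.8 |
| 60% | 1.6% | 7.8% | 2.7 |

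At 0.90 vs 0.75, rejection is at most 3.0% for the same true proportions.

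**5. Two reasons why step 4 is an upper picture**

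- It treats all 15 per arm as outpatients. If half were inpatients with complete capture (assumed), 0.90 vs 0.60 gives (0.5 + 0.5 × 0.90) ÷ (0.5 + 0.5 × 0.60) = 0.95/0.80 = 1.19, not 1.50.
- It assumes one event per subject. With three independent events at 0.60 and 0.75, the chance that at least one is reported is 1 − 0.40³ = 93.6% against 1 − 0.25³ = 98.4%, a ratio of 1.05.

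**The case against.** A reader might infer that outpatient event counts rest on the subject's memory alone and are therefore biased between arms. The documents do not support either half of that.

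- **Other sources exist.** Section XI mentions record review and contact with the treating team without limiting these to inpatients. Table 1 repeats the symptom checklist at each visit, has laboratory tests and ECG at Weeks 6, 12 and 13, and examination at Weeks 6 and 12. Secondary aim 3 includes laboratory abnormalities. A representative may take the call.
- **Recall is short during dosing.** Calls ask about the past week. Entry routes are alternatives, and a slow Trails B or a poor self-report score does not show that a subject cannot report a week's symptoms.
- **Timing works against a memory-driven arm difference.** Section X analyses seizures in the first 6 weeks (section IV words that hypothesis at 12 weeks). Titration takes 5 × 4 = 20 of those 42 days, and the memory benefit is hypothesised after 12 weeks of treatment. After Week 12 all subjects are off drug, so an arm difference would need a benefit that persists.
- **Unawareness of a seizure** is not shown to vary with verbal learning, so it argues for missed events in both arms, not for a difference.
- **The plan is candid.** It calls the trial exploratory and says that definitive anticonvulsant information is out of scope.

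All of this stands against a firm claim of bias by arm. It does not close the gap in ascertainment. Laboratory tests, ECG and examination cannot recover a past seizure or a bout of vomiting, and the outpatient items do not specify record review. The coordinator's contact two weeks before a visit is described as a scheduling contact. The instruction to call about serious events still goes to subjects only.

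**Conclusion.** The concern holds as a gap in ascertainment. Outpatient events come mainly from a call with one respondent, no second informant is routinely asked, and serious events in the nominal 11- to 16-week gaps after dosing depend on the subject calling in or recalling them at the next contact. Under-reporting is a realistic risk in this population, and seizures are the clearest case because a household member may witness what the subject does not know about. At 15 per arm, with sparse cells expected by the plan itself, one or two missed subjects matter.

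A difference between arms is conditional: the drug would have to change memory enough to affect short-interval recall. The documents give no event rates or reporting rates, so neither the loss nor any bias can be sized from them. The ratios of 1.125 to 1.50 illustrate assumed values and are not estimates. The planned sample size is unaffected. This is a worthwhile, inexpensive improvement and not a flaw that invalidates the trial.

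**What to change.** Amend section VIII (Study Design and the monitoring text after Table 1) and section XII (Baseline Symptom Checklist, Drug Side Effects Checklist, Seizure Log, Adverse event monitoring).

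1. On each weekly outpatient call and at Weeks 24, 36 and 52, put the same symptom, side-effect, adverse-event and seizure questions to the subject and, where one is available and the subject agrees, to a caregiver or household member.
2. Record who reported each event and whether an informant was available. Tabulate both by arm.
3. Report counts by arm twice: from subject report alone, and from either source.
4. Give the informant the instruction to call about serious events as well.

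The cost is protocol wording and a few more minutes on contacts already planned, with no added staff or visits. The sections on drug administration, the medication log and compliance already give caretakers a role, so many informants should be reachable. Permission to speak to the informant is needed, and some subjects will have none. Availability may also be unbalanced at 15 per arm, which would make the either-source count uneven; the tabulation and the subject-only count would show this.

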In designing this exploratory study, we conducted a sensitivity analysis to obtain a sample size that would provide a reasonable effect size when comparing Huperzine A to placebo (Figure 2). This allows for detection of differences between the two treatments, to plan for further studies. Assuming a power of 80% and an alpha of 5%, we originally projected that a sample of 60 patients (30 patients in each group) would allow us to detect an effect size of 0.75 between the two groups (placebo and active). Given our prior studies in TBI and cognition, an effect size of 0.75 for the primary outcome measure (CVLT-II) is clinically meaningful, to compare two treatments.

The authorized addition of two self-report measures to our outcome assessment battery (i.e., Cognitive Function subscale from the Neurological Quality of Life Questionnaire and the Ruff Neurobehavioral Inventory) was expected to influence our original power estimate and required sample size. We calculated our effect size by estimating the upper and lower limits of the change score that would be demonstrated by the control group on our primary outcome measure (i.e., California Verbal Learning Test-II). This analysis showed that, to achieve an effect size of 0.75, the final sample size could vary between 15 and 39 subjects per group, given a mean difference

in performance between groups of 3.59 with a standard deviation of 3.30 to 5.13. In view of the variability in this estimate, we proposed that we would run 10 subjects, determine the degree of variability in performance and then adjust the sample size accordingly.

After enrolling 10 subjects, we assessed the data for an estimate of the average difference between groups (difference to baseline) on a ratio of 3:6. There was an estimated effect size of 1.19 between group A (M=4.67, SD=4.51) and group B (M=0.33, SD=2.50). Using a two sample t-test to detect the difference between groups, a minimum sample of 26 subjects will be required (13 per group).

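### The trial was resized on an observed between-group effect of 1.19 in apparently 9 subjects; at the reduced size, power for the standardized 0.75 that the plan calls clinically meaningful is about 45% to 51%, and the visible text does not say so

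*Combined protocol and SAP*

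**What the plan says.** All of this is in Section X (Statistical Analysis) of the combined protocol and SAP, which sizes the trial in three steps.

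- **Original target.** With 80% power and 5% alpha, "we originally projected that a sample of 60 patients (30 patients in each group) would allow us to detect an effect size of 0.75". The plan adds that "an effect size of 0.75 for the primary outcome measure (CVLT-II) is clinically meaningful, to compare two treatments".
- **Intermediate range.** After two self-report measures were added, the plan says that "to achieve an effect size of 0.75, the final sample size could vary between 15 and 39 subjects per group". The inputs are a mean difference "in performance between groups of 3.59 with a standard deviation of 3.30 to 5.13". Because this range was wide, "we proposed that we would run 10 subjects, determine the degree of variability in performance and then adjust the sample size accordingly".
- **Resizing.** After 10 subjects were enrolled, "we assessed the data for an estimate of the average difference between groups (difference to baseline) on a ratio of 3:6". The reported result is: "There was an estimated effect size of 1.19 between group A (M=4.67, SD=4.51) and group B (M=0.33, SD=2.50"). From this: "Using a two sample t-test to detect the difference between groups, a minimum sample of 26 subjects will be required (13 per group").

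Section X then raises 13 to 15 per group (30 in total) for about 15% loss to follow-up. All tests are two-sided at 5%. The comparison for the primary aim is a t-test on the change from baseline to Week 12. Section X describes the study as exploratory, meant to yield effect sizes and variances for later trials.

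**The concern.** The plan named an effect worth detecting and proposed to adjust the sample size once variability was better known. The reported calculation uses the observed difference between the groups as well as the interim SDs, so a small-sample estimate of the treatment effect took the place of 0.75 as the planning target. The only power figure in the visible text is still the 80% for 0.75 at the original 60 patients. A reader could finish the section believing that 30 patients serve the same target.

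What is at stake is how the result is read. If power for 0.75 is near one half, a non-significant primary result says little about whether an effect of that size exists. It could still discourage a later trial, although informing later trials is this study's stated purpose.

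**Working it through.** **Inputs**, all from Section X: two-sided alpha 0.05; 80% power (stated for the original size and assumed to carry over, since the resizing sentence gives none); target 0.75; planning difference 3.59 with SD 3.30 to 5.13; interim means 4.67 and 0.33 with SDs 4.51 and 2.50; ratio 3:6. Power is for the two-sample t-test (noncentral t) with equal groups.

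**1. The plan's own figures.**
- Original size: 0.75 at 80% power needs 28.9, so 29 per group. At 30 per group power is 81.5%. The 60 reproduces.
- Interim effect: 4.67 - 0.33 = 4.34; unweighted SD = sqrt((4.51² + 2.50²)/2) = 3.646; 4.34/3.646 = 1.19. Reproduces.
- Resizing: 1.19 at 80% power needs 12.1, so 13 per group (power 82.9%). Reproduces.

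**2. Power for 0.75 at the reduced size.**
- 13 per group: 45.1%. 15 per group: 50.9%.
- 15 enrolled per group with 15% lost leaves 15 × 0.85 = 12.75, where power is 44.3%. The upper figure therefore needs every enrolled subject to contribute.
- Effect detectable with 80% power: 1.15 at 13 per group, 1.06 at 15.

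**3. Which interim group had 3 subjects.** The ratio 3:6 sums to 9, although 10 were enrolled, and the text does not match the numbers to the groups. If change scores are whole points (an assumption), the reported values identify the split:
- A = 3 fits: sum 14, sum of squares 106, mean 14/3 = 4.67, SD = sqrt((106 - 14²/3)/2) = 4.51.
- B = 6 fits: sum 2, sum of squares 32, mean 2/6 = 0.33, SD = sqrt((32 - 2²/6)/5) = 2.50.
- No other group size from 2 to 7 reproduces either pair of values.

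**4. Precision of the interim estimate (A = 3, B = 6).**
- Pooled SD = sqrt((2 × 4.51² + 5 × 2.50²)/7) = 3.21.
- Standard error = 3.21 × sqrt(1/3 + 1/6) = 2.27; t (7 df) = 2.365.
- 95% CI = 4.34 ± 2.365 × 2.27, about -1.0 to 9.7 points.
- The 95% CI for the SD (chi-square, 7 df) is 2.1 to 6.5. It contains the whole planning range of 3.30 to 5.13, so the interim data did not settle variability either.

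**5. The same sizes judged on the 3.59-point difference.**

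| SD | 3.59/SD | Per group for 80% | Power at 13 | Power at 15 |
|---|---|---|---|---|
| 3.21 (interim, A = 3, B = 6) | 1.12 | 14 | 78% | 84% |
| 3.30 (planning, low) | 1.09 | 15 | 76% | 82% |
| 5.13 (planning, high) | 0.70 | 34 | 40% | 46% |

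**6. The range of 15 to 39.** The table shows that 3.59 points over the stated SDs is 1.09 to 0.70, and needs 15 to 34 per group at 80% power. The 15 reproduces and the 39 does not. The difference equals 0.75 only at SD 3.59/0.75 = 4.79, and 0.75 itself needs 29 per group. The figure 39 would fit 0.75 at 90% power (38.3, rounded up), but the text does not say so.

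**The case against.** The strongest reply is that the route the plan proposed would have ended in almost the same place. Keeping 3.59 points and updating only the SD gives 14 per group with A = 3 and B = 6, against 13 chosen and 15 enrolled. This stands, and it limits the point: the shortfall is against the standardized 0.75, and on raw points it depends on the SD. A reader might infer that the trial is underpowered on any scale, or that resizing on variability would have led to a much larger trial. The figures support neither.

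Other replies also stand in part.
- The standardized 1.19 already contains the interim SDs, so variability was used, though not alone.
- Section X does give power for 0.75, at the original size. What is absent from the visible text is power at the reduced size. Figure 2 relates effect size to sample size, is not visible here, and may show it.
- Section IX names baseline covariates for the primary analysis, whereas Section X makes the t-test the primary comparison and the covariate model secondary. Adjustment could raise power: with an assumed R² of 0.1 to 0.3, power for 0.75 at 13 per group would be about 49% to 59%. That is still well short of 80%.
- The study is labelled exploratory and the basis of its size is openly stated. This lowers the severity, but readers still need to know what the reduced size can detect.

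Two further inferences should be resisted. One is that 13 per group breaches the plan's own lower limit of 15: the range is itself inconsistent, so it is no yardstick, and enrolment equals that limit. The other is that the interim look damaged the 5% level: the plan states no resizing rule, so any size put on that would rest on invented bounds.

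**Conclusion.** The point holds as a should-fix matter of stated power, not as an arithmetic error in the resizing: 1.19 and 13 per group both reproduce. At 13 to 15 evaluable subjects per group, the trial has about a 45% to 51% chance of detecting the standardized effect that the plan calls clinically meaningful, against 81.5% at 30 per group. The visible text of Section X does not tell the reader this. The planning input was a between-group estimate too imprecise to replace a prespecified target. Separately, the range of 15 to 39 per group does not follow from its stated inputs at 80% power.

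The power figures assume an unadjusted two-sided 5% t-test with equal groups. The confidence interval and the interim SD of 3.21 assume A = 3 and B = 6, which rests on whole-point change scores.

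**What to change.** Revise the sample size text in Section X to:

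- state that 13 to 15 evaluable subjects per group give 80% power for a standardized difference of about 1.15 to 1.06, and about 45% to 51% power for 0.75 (unadjusted two-sided 5% t-test);
- give the power for 3.59 points over SDs of 3.30 to 5.13: 76% to 40% at 13 per group and 82% to 46% at 15;
- correct or explain the range of 15 to 39 per group, including the power it assumes and how it relates to 0.75;
- say that the size was set from a comparative interim estimate of the effect, and give the number of subjects in each interim group;
- refer to Figure 2 if it already shows the detectable effect at 26 to 30 subjects.

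Also state that the primary result will be reported as the difference with its 95% confidence interval, and that a non-significant result will not be read as evidence of no effect.

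The cost is wording only, with no change to enrolment or conduct. The downside is that the stated power looks less favourable.
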